9.2.3 Study visits

Not applicable

9.2.4 Study discontinuation

Boehringer Ingelheim reserves the right to discontinue the study at any time for the following reasons:

1. Violation of Good Pharmacoepidemiology Practice (GPP), the study protocol, or the contract by a study site, investigator or research collaborator, disturbing the appropriate conduct of the study

9.3 VARIABLES

9.3.1 Exposures

Exposure of this study is defined as new initiation of Tiotropium/Olodaterol, or ICS/LABA during the study period.

9.3.2 Outcomes

9.3.2.1 Primary outcomes

- Outcome type: Primary
- Outcome Name: Time to the first moderate or severe COPD exacerbations after index date
- Time Frame: 2014~2019Safety Issue (Yes/No): No

NIS Protocol Page 25 of 48 BI Study Number: 1237-0110 c38660249-01

Proprietary confidential information © 2022 Boehringer Ingelheim International GmbH or one or more of its affiliated

9.3.2.2 Secondary outcomes

- Outcome type: Secondary

- Outcome Name: Time to triple therapy escalation after index date

Time Frame: 2014~2019Safety Issue (Yes/No): No

- Outcome type: Secondary

- Outcome Name: Incidence rate of triple therapy initiation (first event per patient)

Time Frame: 2014~2019Safety Issue (Yes/No): No

- Outcome type: Secondary

- Outcome Name: Time to the first hospitalization for community-acquired pneumonia after entry

Time Frame: 2014~2019Safety Issue (Yes/No): No

- Outcome type: Secondary

- Outcome Name: Annualized rate of prescriptions of rescue medications after the index date

- Calculation: annualized rate=number of prescriptions/total patient year at risk=number of prescriptions per patient year

Time Frame: 2014~2019Safety Issue (Yes/No): No

- Outcome type: Secondary

- Outcome Name: Annualized rate of moderate or severe COPD exacerbation after the index date

- Calculation: annualized rate=number of moderate or severe COPD exacerbations/total patient year at risk=number of exacerbations per patient year

Time Frame: 2014~2019Safety Issue (Yes/No): No

9.3.3 Covariates

Demographic characteristics and cohort entry information:

Sex

NIS Protocol Page 26 of 48 BI Study Number: 1237-0110 c38660249-01

Proprietary confidential information © 2022 Boehringer Ingelheim International GmbH or one or more of its affiliated

- Age
- Calendar year of cohort entry
- Season of index date (winter, spring, summer, fall)

Additional, the following clinical characteristics will be measured during the 1 year pre-index baseline period:

Previous COPD treatments

- ➤ LAMA monotherapy
- ➤ LABA monotherapy
- > ICS monotherapy
- ➤ LAMA/ICS combination therapy

Use of other respiratory drugs

- Mucolytics
- > Theophylline
- ➤ Short-acting beta-agonists
- > Short-acting muscarinic antagonists
- Previous acute COPD exacerbation (measured both 12 months and in the 30 days prior to cohort entry), categorized as 0, 1 or 2+.
 - ➤ All exacerbations (Moderate+Severe)
 - An outpatient visit with a diagnosis code for COPD in any field + a prescription for an oral corticosteroid or an antibiotic for respiratory infections (Moderate)
 - ➤ Hospitalizations or emergency room visits with a primary diagnosis for COPD (Severe)
- Hospitalizations caused by exacerbation of COPD in 12 months prior to the index date:
 - **>** 0;
 - **>** 1;
 - **>** 2+;
- all-cause hospitalizations in 12 months prior to index date:
 - > 0;
 - **>** 1;
 - **>** 2+;
- Comorbidities:
 - > Cardiovascular disease
 - > Cerebrovascular disease
 - Diabetes
 - > Chronic kidney disease
 - > Pneumonia
 - > Cancer
 - Cirrhosis

NIS Protocol Page 27 of 48 BI Study Number: 1237-0110 c38660249-01

Proprietary confidential information © 2022 Boehringer Ingelheim International GmbH or one or more of its affiliated

- Charlson Comorbidity Index (CCI)
- History of medications dispensed in the 12 months before or on the index date will be identified from the pharmacy dispensing history:
 - > Cardiovascular drugs:

Antihypertensives

Antiarrhythmics

Nitrates

heart failure medications

- ➤ Lipid-lowering medications
- ➤ Blood glucose-lowering medications
- ➤ Anticoagulants and antiplatelet agents
- > Antibiotics
- ➤ Antineoplastic agents

COPD severity

The definition of the severity of COPD in this study was developed based on the information in previous studies, GOLD recommendations and clinical practice in Taiwan, see below. Patients who fulfil criteria for more than one category will be classified as being in the most severe category.

Criteria of COPD severity:

➤ Mild:

Naïve to COPD treatment, or at least one dispensing of the following categories of medications either alone or in combination: 1) SABA or SAMA or SABA+SAMA, 2) LAMA or LABA monotherapy, 3) theophylline or mucolytics, in the 12 months before the index date;

➤ Moderate:

At least one dispensing of LAMA + LABA in the 12 months before the index date;

> Severe:

Occurrence of at least one of the following events in the 12 months before the index date:

- Hospitalisation for COPD
- Recorded diagnosis of pneumonia
- Second course of antibiotics for respiratory tract infections
- Second course of systemic corticosteroids for the treatment of COPD exacerbation
- Two diagnoses of COPD exacerbation without hospitalisation

➤ Very severe:

Occurrence of at least one of the following events in the 12 months before the index date unless other time period is specified:

- Dispensed oxygen therapy
- Dispensed nebuliser therapy

NIS Protocol Page 28 of 48 BI Study Number: 1237-0110 c38660249-01

Proprietary confidential information © 2022 Boehringer Ingelheim International GmbH or one or more of its affiliated

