9.5 STUDY SIZE

Based on the result of study by Wedzicha JA, et al, [P16-05628] (where at least 25% of the patients in the Tio/Olo group have a first moderate or severe exacerbation at 127 days [95% CI, 107 to 149] and in ICS/LABA group at 87 days [95% CI, 81 to 103] (HR = 0.78, [95% CI 0.70 to 0.86])), we assume that at least 25% of patients in the ICS/LABA experienced a first moderate or severe COPD exacerbation at 103 days and the HR of Tio/Olo to LABA/ICS is 0.9. For a study duration of 6 years, a total of 4978 patients (2489 patients each arm) are needed to detect the difference between the two arms with 2-sided alpha of 0.05 and 90% power

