## **6. RESEARCH METHODS**

### **6.1 STUDY DESIGN**

This study will be a non-interventional cohort study using Taiwan National Health Insurance (NHI) claims database, Taiwan Cancer Registry (TCR) and Taiwan Mortality Data. It is a secondary health data environment with relevant information on treatment and disease outcomes of COPD patients among a population of predominantly ethnic Han Chinese. As a publicly funded single payor health insurance program, a wide range health services, including hospital care, emergency visits, ambulatory clinic services, and prescription drugs are covered for virtually all Taiwan residents. The complete capture of health care encounters reimbursed by NHI among a defined group of patients has served as the basis of many longitudinal studies that evaluated safety profiles of prescribed medications.

Health data that are available for research are provided by the Health and Welfare Data Science Center (HWDSC) of the Department of Statistics, Ministry of Health and Welfare. The HWDSC staff encrypt the national ID for all individuals according to a secure encryption algorithm that is specific for each study, and the encrypted ID all individuals is used for linkage between databases. While the study will provide safety data on drugs of interest, from a regulatory perspective the source data are not auditible, nor de-identified individual level data be brought outside of HWDSC for independent verification of analysis.

Limitations of health insurance databases are well-known, as there is no information on results of clinical parameters (such as blood pressure and body mass index), clinical examinations (such as spirometry findings), or life style attributes (such as smoking). A specific items that needs to be considered for this particular study project is whether the findings are generalizable to COPD patients in China. While there is high similarity between COPD patients in Taiwan and those in China in terms of ethnicity and dietary patterns, management patterns for COPD patients, including comorbid conditions, concomitant medications, and use of traditional Chinese medication regimens, may be different.

Taking into account the strengths and potential limitations of the data source, the population-based nature and potentially large study size of patients on drugs of interest are the major reasons that this data source is a viable option for the study.

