### **7.2 OUTCOMES**

#### **7.2.1 Primary outcomes**

##### **➤ Time to the first moderate or severe COPD exacerbations after index date**

The definition of moderate or severe COPD exacerbation:

- a. Moderate exacerbations will be defined as an outpatient visit with a diagnosis code for COPD in any field + a prescription for an oral corticosteroid or an antibiotic for respiratory infections
- b. Severe exacerbations will be defined as a hospitalization or emergency room visit with a primary diagnosis for COPD

Detailed diagnosis codes are listed in Annex.

Tio/Olo users will be matched to the comparator through 1:1 propensity score matching. For the analysis of the primary outcome, individuals will be followed up from the index date until the first moderate or severe COPD exacerbation. For detailed, please refer to section [10.1](#). As time-to-event data, the main analysis will be univariate proportional hazard regression analysis to estimate the hazard ratio (Tio/Olo vs. comparator) and its 95% confidence interval (CI). Detailed analytic approach is described in Section [10.1](#).

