# BOEHRINGER INGELHEIM Group of Companies

## Statistical and Epidemiological Analysis Plan (SEAP) for Non-Interventional Studies (NIS)

c40729787-01

Page 24 of 38

Proprietary confidential information © 2022 Boehringer Ingelheim International GmbH or one or more of its affiliated companies

	Before propensity score match				After propensity score match					
	Tio/Olo cohort		ICS/LABA cohort		ASD	Tio/Olo cohort		ICS/LABA cohort		
	N	%	N	%		N	%	N	%	
Acute COPD exacerbation in 1 year prior to index date										
Moderate exacerbation										
0										
1										
>=2										
Severe exacerbation										
0										
1										
>=2										
All exacerbations (Moderate + Severe)										
0										
1										
>=2										
Acute COPD exacerbation in the 30 days prior to index date										
Moderate exacerbation										
0										
1										
>=2										
Severe exacerbation										
0										
1										
>=2										
All exacerbations (Moderate + Severe)										
0										
1										
>=2										
Hospitalizations caused by exacerbation of COPD in 1 year prior to index date										
0										
1										
>=2										
All-cause hospitalizations in 1 year prior to index date										
0										

Proprietary confidential information © 2022 Boehringer Ingelheim International GmbH or one or more of its affiliated companies

	Before propensity score match				After propensity score match					
	Tio/Olo cohort		ICS/LABA cohort		ASD	Tio/Olo cohort		ICS/LABA cohort		ASD
	N	%	N	%		N	%	N	%	
1										
>=2										

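### Moderate exacerbations are recorded only at outpatient visits, yet no outpatient visit count is among the covariates, so a residual difference in prior visit frequency would go unseen and unadjusted

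*Protocol*

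**What the plan says.** SAP 7.2.1 defines a moderate exacerbation as "an outpatient visit with a diagnosis code for COPD in any field" together with an oral corticosteroid or a respiratory antibiotic. A severe exacerbation is a hospital admission or emergency room visit with COPD as the primary diagnosis. The primary endpoint is the first of either.

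On general health-care use, Protocol 9.3.3 lists "all-cause hospitalizations in 12 months prior to index date" in three classes (0, 1, 2+), and the SAP Table 1 shell has the matching row, "All-cause hospitalizations in 1 year prior to index date". Cause-specific hospitalizations are listed as well. No count of outpatient visits, for any cause or for COPD, appears in Protocol 9.3.3, SAP 7.3 or Table 1. The data exist: SAP 6.1 says that "hospital care, emergency visits, ambulatory clinic services, and prescription drugs are covered" for nearly all residents.

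Under SAP 10.1 the propensity score uses every listed covariate except season, and the match is run a single time. The Cox model has treatment alone, and a listed covariate enters only if its standardized difference exceeds 0.1. Protocol 9.7.1 speaks of further predictors in the model but names none. The limitations in Protocol 9.9 and SAP 6.1 do not mention visit frequency.

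**The concern.** COPD may be coded in any position on the claim, and the qualifying drugs in SAP Appendix 5 are broad classes with no recorded indication. A visit for another disease, with COPD as a secondary code and an antibiotic prescribed, can therefore count as a moderate event. Patients who attend more often have more chances to be counted at the same underlying disease activity.

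If the matched arms differ in how often they attend, the primary hazard ratio partly measures attendance. The plan could not reveal this: an unlisted variable is not matched on, does not appear in the balance table and cannot trigger the adjustment rule. The planned effect is small ("the HR of Tio/Olo to LABA/ICS is 0.9"), so a modest shift would matter.

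**Working it through.** **The plan's own figure.** Protocol 9.5 assumes that "at least 25% of patients in the ICS/LABA experienced a first moderate or severe COPD exacerbation at 103 days", that "the HR of Tio/Olo to LABA/ICS is 0.9", and a design "with 2-sided alpha of 0.05 and 90% power".

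- Events (Schoenfeld): 4 × (1.960 + 1.282)² / (ln 0.9)² = 3,787.
- ICS/LABA hazard: −ln(0.75)/103 = 0.002793 per day, multiplied by 0.9 for Tio/Olo.
- "For a study duration of 6 years" leaves the split between entry and follow-up open. Uniform entry over 6 years without loss gives N = 4,574. The same entry with an unstated loss of 10% per year gives 4,972, close to the stated 4,978. The stated size is under-specified but not shown to be wrong, and this point does not depend on it.

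**Effect of visit frequency.** The documents give neither visit rates by arm nor the moderate share of events, so the following are assumptions:

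- d: relative excess of visits in one arm that remains after matching; 0.05, 0.10, 0.15.
- e: elasticity of the recorded moderate-event hazard to visit frequency; 0.3 to 1.
- s: moderate share of first events; 0.5 to 0.9.
- Constant hazards, and severe events unaffected by outpatient visits.

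The recorded moderate-event hazard is multiplied by (1+d)^e. Only the share s of the composite hazard is affected, so the composite is multiplied by s(1+d)^e + 1 − s. The shift is s × [(1+d)^e − 1].

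| d | Moderate-event hazard, e = 0.3 to 1 | Composite, s = 0.5 | Composite, s = 0.9 |
|---|---|---|---|
| 5% | 1.5% to 5% | 0.7% to 2.5% | 1.3% to 4.5% |
| 10% | 2.9% to 10% | 1.5% to 5% | 2.6% to 9% |
| 15% | 4.3% to 15% | 2.1% to 7.5% | 3.9% to 13.5% |

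The smallest entry is 0.5 × (1.05^0.3 − 1) = 0.7%. The largest is 0.9 × 0.15 = 13.5%. More visits in the Tio/Olo arm raise its hazard ratio. More visits in the ICS/LABA arm lower it.

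**What that does to the test.** Let r be the Tio/Olo to ICS/LABA ratio of the chance that a moderate event is recorded. The recorded hazard ratio is the true one × (s·r + 1 − s). Take a true hazard ratio of 1.0, s = 0.8 and 3,787 events:

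- r = 0.95: recorded 0.8 × 0.95 + 0.2 = 0.96, with about a 24% chance of rejecting at the two-sided 5% level.
- r = 0.90: recorded 0.92, with about a 73% chance.

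For a null effect to be recorded as 0.90, r = 1 − 0.1/s is needed: 0.89 at s = 0.9 and 0.80 at s = 0.5.

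**The case against.** **No difference is shown.** Nothing in the documents indicates that the arms attend at different rates, in either direction. What matters is the difference left after matching, and several listed covariates reduce it: prior exacerbations over 12 months and 30 days, comorbidities that can be met by more than two outpatient diagnoses (SAP Appendix 4), a year of drug history, the Charlson index, and severity criteria based on repeat courses and COPD exacerbation diagnoses. This stands, and it lowers the plausible value of d. But these variables record the presence of a disease or a prescription. Exacerbation counts stop at 2+ and omit visits without a qualifying drug. None measures how often a patient is seen.

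**The size is easily overstated.** A reader might apply the full 1.5% to 15% to the primary hazard ratio. That range belongs to the moderate component only. Severe events need no outpatient visit, so the composite moves by s times as much. An elasticity of 1 is also an extreme, since a visit counts only with a COPD code and a qualifying prescription.

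**Rescue medication.** A reader might extend the argument to the rescue-prescription rate on the ground that each prescription needs a visit. The documents do not say so. SAP 7.2.2 (4) defines that outcome by drug, without an outpatient visit, and Protocol 9.4 says that inpatient drug use is available too.

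**A baseline count is not a full remedy.** The recording happens after the index date. A baseline count balances prior habits but not visit differences that arise later. The common 45-day gap rule may narrow those differences. This stands and limits what the fix can claim.

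**A check already exists.** SAP Table 2 reports a separate severe-exacerbation hazard ratio. It is useful, but it is not designated as a check and does not repair the primary estimate. Redacted SAP sections may hold other analyses and are not counted as missing here. The covariate lists and the propensity score rule are visible.

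**Conclusion.** The gap is real and limited. Outpatient visit frequency feeds directly into the moderate part of the primary endpoint, is available in the claims, and is not matched, checked or adjusted. Existing covariates cover it only in part.

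Size and direction are unknown. Under the assumed ranges (5% to 15% more visits after matching, elasticity 0.3 to 1, moderate share 50% to 90%) the composite hazard ratio moves by about 0.7% to 13.5%, against a planned effect of 10%. The lower end is negligible. The upper end could create or hide the planned effect.

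A reader might infer that the primary result is biased, or biased in a known direction. The documents do not support that. They support only that the plan could not detect or adjust for such a difference. Because the match is run a single time, the matter should be settled before it.

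**What to change.** - Add two covariates to Protocol 9.3.3, SAP 7.3 and SAP Table 1: the number of all-cause outpatient visits and the number of COPD-coded outpatient visits in the 12 months before the index date, as log(1+n) or in quintiles.
- Enter both in the propensity score and in the standardized-difference check before matching.
- State that this balances prior visit habits and not visit differences arising after the index date.
- Designate the severe-only hazard ratio in SAP Table 2 as the check on residual detection bias, and say beforehand how a divergence from the composite would be read.

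While these lists are open, reconcile one entry: SAP 7.3 has heart failure hospitalizations where Protocol 9.3.3 and SAP Table 1 have COPD hospitalizations.

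The cost is two derived counts from claims the study already uses, a few lines of text and the added Table 1 rows. The stated sample size does not change. A few more Tio/Olo patients may go unmatched within the caliper.

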### 7.3 COVARIATES

Demographic characteristics and cohort entry information:

- Sex
- Age
- Calendar year of cohort entry
- Season of index date (winter, Dec-Feb; spring, Mar-May; summer, Jun-Aug; fall, Sep-Nov )

Additional characteristics will be defined during the 1-year pre-index baseline period:

- Previous COPD treatments
  - LAMA monotherapy
  - LABA monotherapy
  - ICS monotherapy
  - LAMA/ICS free combination therapy
- Use of other respiratory drugs
  - Mucolytics
  - Theophylline
  - Short-acting beta-agonists
  - Short-acting muscarinic antagonists
- Previous acute COPD exacerbation (measured both 12 months and in the 30 days prior to cohort entry), categorized as 0, 1, or 2+.
  - All exacerbations (Moderate+Severe)
  - An outpatient visit with a diagnosis code for COPD in any field + a prescription for an oral corticosteroid or an antibiotic for respiratory infections (Moderate); prescriptions within 30 days of each other were considered as continuation of the initial exacerbation.
  - Hospitalizations or emergency room visits with a primary diagnosis for COPD

(Severe); hospitalizations or emergency room visits within 30 days of each other were considered as continuation of the initial exacerbation.

- Hospitalizations caused by exacerbation of heart failure in 12 months prior to index date, categorized as
  - 0;
  - 1;
  - 2+.
- All-cause hospitalizations in 12 months prior to index date;
  - 0;
  - 1;
  - 2+.
- Comorbidities:
  - Cardiovascular disease
  - Cerebrovascular disease
  - Diabetes
  - Chronic kidney disease
  - Pneumonia
  - Cancer
  - Cirrhosis
- Charlson Comorbidity Index (CCI)
- History of medications dispensed in the 12 months before or on the index date will be identified from the pharmacy dispensing history:
  - Cardiovascular drugs:
    - antihypertensives;
    - antiarrhythmics;
    - nitrates;
    - heart failure medications
  - Lipid-lowering medications
  - Blood glucose-lowering medications
  - Anticoagulants and antiplatelet agents
  - Antibiotics
  - Antineoplastic agents
- COPD severity

The definition of the severity of COPD in this study was developed based on the information in previous studies, GOLD recommendations and clinical practice in Taiwan, see below. Patients who fulfil criteria for more than one category will be classified as being in the most severe category.

Operational definition of COPD severity:

- Mild:

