Naïve to COPD treatment, or at least one dispensing of the following categories of medications either alone or in combination: 1) SABA or SAMA or SABA+SAMA, 2) LAMA or LABA monotherapy, 3) theophylline or mucolytics, in the 12 months before the index date;

- Moderate:  
At least one dispensing of LAMA + LABA in the 12 months before the index date;
- Severe:  
Occurrence of at least one of the following events in the 12 months before the index date:
  - Hospitalization with a primary diagnosis for COPD
  - Hospitalization with a primary diagnosis for pneumonia
  - Second course of antibiotics for respiratory tract infections; a single course of antibiotic treatment involving multiple dispensings is defined as that involving consecutive dispensings of antibiotics with fewer than 7 days between the end of days of supply of one dispensing and the date of the next dispensing
  - Second course of systemic corticosteroids for the treatment of COPD exacerbation; a single course of systemic corticosteroids involving multiple dispensings is defined as that involving consecutive dispensings with fewer than 7 days between the end of days of supply of one dispensing and the date of the next dispensing.
  - Two diagnoses of COPD exacerbation (ICD-10: J44.1; ICD-9: 491.21) without hospitalisation
- Very severe:  
Occurrence of at least one of the following events in the 12 months before the index date unless other time period is specified:
  - Dispensed oxygen therapy
  - Dispensed nebuliser therapy

Diagnosis codes and drug codes are listed in the annex.

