## **10. DATA ANALYSIS**

### **10.1 MAIN ANALYSIS**

All variables, including patient characteristics, baseline measures, and outcomes, will be analyzed descriptively.

- For all analyses, variables will be reported as follows: Continuous variables (e.g., age) will be presented as means (with standard deviation, SD) and/or medians (with interquartile range, IQR), minimum, maximum.

- Categorical variables (e.g., sex) will be presented as absolute and relative frequencies.

All analyses will be presented for each treatment group (Tio+Olo vs LABA/ICS) overall. We will first describe formation of the study cohort. Propensity score (PS) matching will be used to generate two comparable treatment groups. All covariates, except season of index date, will be used to estimate the propensity score with logistic regression. Patients in LABA/ICS group will be individually matched to patients in the Tio/Olo group with 1:1 ratio. A caliper of 0.06 standard deviation of logit (propensity score) will be used to define the range of estimated PS within which to select the comparator. Within that range the LABA/ICS patient with the closest estimated propensity score to the Tio/Olo patient will be selected.

Patient characteristics at baseline in patients treated with Tio+Olo and patients treated with LABA/ICS will be described separately using standard descriptive statistics after propensity score matching. Absolute standardized differences (ASDs) will be used to compare the characteristics between the two groups after propensity score matching, in which a  $>0.1$  ASD indicates a meaningful difference.

All the analyses for primary outcome and secondary outcomes will be performed on patients after propensity score matching. Baseline characteristic table shell are provided in [Table 1](#). The propensity score matching will be carried out once without re-matching.

For the analysis of the primary outcome, individuals will be followed up from the index date until the first moderate or severe COPD exacerbation. The data after the earliest date of the following event would be censored:

- 1) disenrollment
- 2) the end of the study period
- 3) death
- 4) discontinuation of index drug use (a lapse of 45 days without subsequent prescription)
- 5) switching from Tio/Olo to ICS/LABA or from ICS/LABA to Tio/Olo
- 6) escalation to triple therapies (ICS/LAMA/LABA free or fix dose combination)

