## Appendix 5. Drugs of interest

Groups	ATC code
Use of other respiratory drugs	
Mucolytics	R05CB, R05CB01, R05CB02, R05CB03, R05CB04, R05CB05, R05CB06, R05CB10, R05CB11, R05CB91, R05CB92
Theophylline	R03DA04, R03DA54, R03DA74, R03DB04
SABA	R03AC02, R03AC03, R03AC04, R03AC06
SAMA	R03BB01
SABA/SAMA	R03AL01, R03AL02
Drugs for COPD exacerbation treatment	
Oral corticosteroid	H02AB01, H02AB02, H02AB04, H02AB05, H02AB06, H02AB08, H02AB10, H02BX, H02BX91
Antibiotic for COPD exacerbation	J01AA02, J01CA04, J01CR02, J01CR05, J01EE01, J01DC01, J01DC02, J01DC03, J01DC04, J01DC05, J01DC06, J01DC07, J01DC09, J01DC14, J01DD01, J01DD02, J01DD04, J01DD05, J01DD06, J01DD07, J01DD08, J01DD12, J01DD13, J01DD14, J01DD52, J01DD62, J01DE01, J01DE02, J01FA01, J01EA02, J01EA03, J01EA06, J01EA07, J01EA08, J01FA09, J01FA10, J01FA15, J01FA91, J01MA01, J01MA02, J01MA03, J01MA04, J01MA06, J01MA07, J01MA09, J01MA12, J01MA14, J01MA15
Drugs for Medication history	

 
● Cardiovascular drugs
 
	
Anti-hypertensives	C02AA01, C02AA02, C02AA04, C02AB01, C02AB02, C02AC01, C02CA01, C02CA04, C02CA, C02CC02, C02DA01, C02DB02, C02DC01, C02DD01, C02LA01, C02LA50, C02LA51, C02LB01, C02LG02, C02N, C03AA01, C03AA03, C03AA06, C03AA07, C03AA, C03BA04, C03BA08, C03BA11, C03CA01, C03CA02, C03CA04, C03CC01, C03DA01, C03DA04, C03DB01, C03DB02, C03EA01, C03EA, C07AA01, C07AA02, C07AA03, C07AA05, C07AA06, C07AA07, C07AA12, C07AA15, C07AA19, C07AB02, C07AB03, C07AB04, C07AB05, C07AB07, C07AB09, C07AB12,

	C07AG01, C07AG02, C07BA68, C07BB02, C07CA03, C07CB03, C07DA06, C08CA01, C08CA02, C08CA03, C08CA04, C08CA05, C08CA07, C08CA08, C08CA09, C08CA12, C08CA13, C08CA15, C08DA01, C08DB01, C09AA01, C09AA02, C09AA03, C09AA04, C09AA05, C09AA06, C09AA07, C09AA08, C09AA09, C09AA16, C09BA01, C09BA02, C09BA04, C09BB04, C09BB05, C09BB, C09BB, C09CA01, C09CA02, C09CA03, C09CA04, C09CA06, C09CA07, C09CA08, C09CA09, C09DA01, C09DA03, C09DA04, C09DA06, C09DA07, C09DA08, C09DA09, C09DB01, C09DB02, C09DB04, C09DB07, C09DX01, C09DX03, C09DX04, C09XA02, C09XA52, C09XA53, C09XA54
Antiarrhythmics	C01AA04, C01AA05, C01AA07, C01AA08, C01AB01, C01AC01, C01BA01, C01BA02, C01BA03, C01BA04, C01BA08, C01BB01, C01BB02, C01BC03, C01BC04, C01BD01, C01BD07, C01CA02, C01CA04, C01CA06, C01EB10, C01EB17, C07AA01, C07AA02, C07AA03, C07AA05, C07AA07, C07AA12, C07AA15, C07AA19, C07AB02, C07AB03, C07AB04, C07AB05, C07AB07, C07AB09, C07AB12, C08DA01, C08DB01

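### Baseline oral corticosteroid use is only partly captured by the planned covariates, so a residual imbalance could shift the primary hazard ratio in either direction without being seen

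*Protocol*

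**What the plan says.** - **Outcome.** SAP 7.2.1 defines a moderate exacerbation as an outpatient visit with a COPD code in any field plus "a prescription for an oral corticosteroid or an antibiotic for respiratory infections". It asks for no new course and no gap since an earlier prescription.
- **Medication history.** Protocol 9.3.3: "History of medications dispensed in the 12 months before or on the index date will be identified from the pharmacy dispensing history". The groups are cardiovascular, lipid-lowering, glucose-lowering, anticoagulant/antiplatelet, antibiotic and antineoplastic drugs. SAP 7.3 and SAP Table 1 repeat them. OCS codes exist in SAP Appendix 5, but only under "Drugs for COPD exacerbation treatment".
- **Covariates that carry some OCS information.** Prior exacerbations use the outcome's own algorithm, are graded 0, 1 or 2+, and are "measured both 12 months and in the 30 days prior to cohort entry". SAP 7.3 adds that "prescriptions within 30 days of each other were considered as continuation of the initial exacerbation". COPD severity places a patient in the severe class for, among other things, a "Second course of systemic corticosteroids for the treatment of COPD exacerbation". SAP 7.3 treats as a single course "consecutive dispensings with fewer than 7 days between the end of days of supply of one dispensing and the date of the next dispensing".
- **Use of the covariates.** SAP 10.1: "All covariates, except season of index date, will be used to estimate the propensity score with logistic regression". Matching is done once. A covariate enters the outcome model only if its absolute standardized difference (ASD) after matching exceeds 0.1.

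**The concern.** Two drug classes can trigger the moderate component of the primary event. One is a baseline covariate in its own right and the other is not, and the plan gives no reason for the difference.

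The patients at issue are those already taking OCS at index. For them, a routine COPD-coded refill visit meets the event definition without any exacerbation. If such users are unevenly spread between the matched arms in a way the listed covariates do not reflect, the primary hazard ratio moves with no drug effect. The plan's safeguard, the ASD check, works only on listed covariates and so cannot detect it.

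**Working it through.** **Step 1. What the existing covariates capture.** OCS at a COPD-coded visit before index counts as a prior moderate exacerbation and so enters the propensity score, pooled with antibiotics. Repeat courses for COPD exacerbation enter through severity. Three things are left out:

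1. OCS dispensed at visits without a COPD code. Inclusion allows the first COPD code to fall on the index date, so earlier OCS can be wholly invisible.
2. OCS kept separate from antibiotics.
3. The intensity of continuous use (Step 2).

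**Step 2. When continuous use is merged.** I counted baseline exacerbations over 365 days for COPD-coded refills at a fixed interval starting on day 0, under two readings of the 30-day rule.

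| Refill interval | Each prescription joined to the previous one | 30 days counted from the first prescription |
|---|---|---|
| 28 or 30 days | 1 | 7 (2+) |
| 31 days | 12 (2+) | 12 (2+) |
| 60 days | 7 (2+) | 7 (2+) |
| 90 days | 5 (2+) | 5 (2+) |

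Only refills 30 days or less apart, under the first reading, collapse to one event. Supply gaps under 7 days also make the year a single course, so the second-course criterion is not met. Such a patient scores 1 at 12 months and 1 at 30 days, which is the same profile as one short burst in the month before index.

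**Step 3. Size.** The documents contain no OCS figure to reproduce, so this step is illustrative.

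- *From Protocol 9.5:* 25% with an event by 103 days. The hazard is −ln(0.75) / 103 × 365.25 = 0.2877 / 103 × 365.25 = 1.02 per year, used for non-users in both arms.
- *Assumed:* true hazard ratio 1; user hazard λ of 4, 8 or 12 per year (a COPD-coded refill visit every 3 months to every month); censoring at the earlier of an exponential time with mean 1 year and a uniform time over 0 to 6 years; p is the prevalence of OCS users that remains after matching.
- *Method:* event-free survival in an arm is (1−p)·exp(−1.02t) + p·exp(−λt). The hazard ratio is the value that solves the Cox score equation for the two arms.
- *ASD:* |p1−p0| / √{[p1(1−p1) + p0(1−p0)]/2}. For 4% vs 6% this is 0.02 / √[(0.0384 + 0.0564)/2] = 0.092.

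| Tio/Olo vs ICS/LABA | ASD | λ = 4 | λ = 8 | λ = 12 |
|---|---|---|---|---|
| 5% vs 5% | 0 | 1.00 | 1.00 | 1.00 |
| 4% vs 6% | 0.092 | 0.976 | 0.968 | 0.966 |
| 3% vs 6% | 0.145 | 0.964 | 0.953 | 0.949 |
| 4% vs 8% | 0.169 | 0.952 | 0.938 | 0.932 |

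A simulation of 1,000,000 patients per scenario agrees to within rounding. Swapping the arms gives the reciprocals, from 1/0.976 = 1.02 to 1/0.932 = 1.07.

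A rougher check uses (1 + p1(g−1)) / (1 + p0(g−1)), where g is the event-rate ratio of users to non-users. For 3% vs 5% and g = 3 it gives 1.06 / 1.10 = 0.964; g = 2 gives 0.981 and g = 5 gives 0.933.

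**The case against.** The strongest reply is that the plan already measures prior OCS use with the endpoint's own definition, over two windows, and adds repeat courses through severity. Much of this stands:

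- The 30-day covariate separates a current refiller from someone whose only burst was months ago.
- COPD-coded refills every 2 to 3 months already score 2+, so the merging mechanism does not support the λ = 4 and λ = 8 columns. Those apply, if at all, to users whose earlier OCS carried no COPD code.
- OCS at a visit without a COPD code is not an event. Excluding asthma, allergic rhinitis, interstitial lung disease and lung transplant removes some non-COPD steroid users.
- The residual imbalance is assumed, as is its direction.

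A reader might also infer that baseline OCS use drives the annualized exacerbation rate by construction. For monthly refillers the documents do not support that, because SAP 7.2.2 (5) applies the same 30-day joining to the outcome.

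These points narrow the gap but do not close it. None of them covers OCS without a COPD code, OCS apart from antibiotics, or refills at 30 days or less. The redacted SAP text after 10.1 may hold further analyses, but it does not change the visible covariate list.

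**Conclusion.** Baseline OCS use is partly captured, and the part left out bears on the primary event definition. With residual imbalances of 2 to 4 percentage points, the primary hazard ratio would shift by about 2 to 7%. In the scenario that fits the merging rule best (monthly refills, λ = 12) the shift is about 3 to 7%. That is material against a design hazard ratio of 0.90. With equal prevalence there is no shift.

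The result rests on assumed prevalences, refill rates and on-treatment time, and on the residual OCS use being independent of the matched covariates.

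A reader might go further and conclude that steroid users are left unbalanced and that the hazard ratio is biased. The documents do not support this: they give no OCS prevalence by arm, and the existing covariates balance some of that use. What can be said is that an imbalance may remain, that its direction is unknown, and that the plan as written could not reveal it. At 4% vs 6% the ASD of 0.092 would not trigger regression adjustment even if OCS were listed, so the main gain there would come from having OCS in the propensity score.

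**What to change.** In Protocol 9.3.3, SAP 7.3 and SAP Table 1, add two medication-history covariates for the 12 months before or on the index date, built from the OCS codes in SAP Appendix 5:

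1. any oral or systemic corticosteroid dispensing, regardless of diagnosis code;
2. long-term or cumulative supply, for example at least 90 days.

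Include both in the propensity score and the ASD check. Because matching is done once, they must be specified before it is run. It would also help to state in SAP 7.3 whether the 30 days run from the first or from the previous prescription.

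The cost is SAP wording, a matching protocol edit and two covariates that partly overlap existing ones. The claims and codes are already held, so no further data or patients are needed.
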